### *On Day of Visit*

- a. Confirm participant's willingness to continue in the research study.
- b. Obtain medication history and concomitant medications. Add to Concomitant and Prior Medications Log.
- c. Verify medication calendar with number of remaining capsules.
- d. Take back medication calendar.
- e. Measure vital signs: height, weight, blood pressure, heart rate, respiration rate, and temperature.
- f. Perform physical exam.
- g. Place indwelling venous catheter to obtain blood samples for safety labs and for atomoxetine pharmacokinetic and pharmacodynamic analysis.
- h. Collect blood samples for the following safety laboratory tests (to be processed immediately at Children's Mercy Hospital): CBC with differential, basic metabolic panel, and liver function test. These tests may be omitted if these data were collected in the week prior, at the discretion of the study coordinator, the physician performing the physical exam or any person designated in the delegation of authority log.
- i. Collect urine for urinalysis with microbiology.
- j. Perform urinary pregnancy test on female subjects 10 years of age or older.

- k. Collect baseline urine sample (~10 mL) for predose urine sample and CYP2D6 biomarker analysis.
- l. Confirm prior to dosing that participant is:
  - i. Healthy enough to continue Research Visit 4 (sign off on safety labs and physical exam sheet by physician).
  - ii. Not pregnant, females only (urine pregnancy test).
  - iii. Has been compliant with medication (medication calendar check). If the participant has not been compliant, the visit will need to rescheduled.
- m. Place two sweat patches on the participant's back. The sweat patch is 15.4 cm^2 in size and consists of a cellulose blotter paper collection pad (PharmChek®, PharmaChem Laboratories, Menlo Park, CA). Prior to patch placement, clean the area of skin to which the patch will be applied with rubbing alcohol.
- n. Collect pre-dose blood, blood pressure, and heart rate prior to dosing medication.
- o. Administer dose of atomoxetine according to prescription.
- p. Collect 3 mL of blood, blood pressure, and heart rate at the following time points after dose administration:
  - i. Timeframe:
    - i. Study Design 1: 0.5, 0.75, 1, 1.5, 2, 3, 4, 6, 8, 10, 12, 16, 20, and 24 hours.
    - ii. Study Design 2: 0.5, 0.75, 1, 1.5, 2, 3, 4, 6, 8, 10, and 12 hours.
    - iii. Study Design 3:
      - 1. Following first dose: Collect at 0.5, 0.75, 1, 1.5, 2, 3, 4, 6, 8, 10, and 12 hours as applicable following first dose and will continue only until the second dose is given.
      - 2. Second dose will be given at the same time increment between when participant routinely takes their first and second dose (eg. If 6 hours are between routine dosing for participant, the second study dose will be given 6 hours after the first dose).
      - 3. Collect predose blood, blood pressure, heart rate prior to dosing 2nd dose
      - 4. Once the second dose is given, continued blood draws, blood

pressure, and heart rate collection based on the timing of the first dose will stop.

5. Timing of blood, blood pressure, and heart rate will now be timed according to second dose only.
6. Timing of collections will restart, with timepoints 0.5, 0.75, 1, 1.5, 2, 3, 4, 6, 8, 12, and 16 hours after the second dose.
  - iv. A window of  $\pm$  5 minutes is acceptable for blood draws at time points 0.5 – 2 hours.
  - v. A window of  $\pm$  15 minutes is acceptable for blood draws at all other time points.

- ii. Collection Instructions: 2 mL of blood will be collected in an EDTA tube and 1 mL of blood will be collected in a serum gel separator tube.
- iii. Processing: Within an hour of collecting sample, plasma and serum will be separated by centrifugation at 4°C (1000 – 2000 g x 10 min), aspirated manually, and transferred to polypropylene cryovials for storage at -70°C until analysis.

- q. Collect and pool urine starting after dose administration.
  - i. Study Design 1: collect all urine for the first 24 hours in the PCRU. Record the volume of urine excreted. Collect a ~10 mL sample and store in 15 mL polypropylene falcon tubes for storage at -70°C until analysis.
  - ii. Study Design 2: collect all urine 12 hours post drug administration. Record the volume of urine excreted. Collect a ~10 mL sample and store in 15 mL polypropylene falcon tubes for storage at -70°C until analysis.
  - iii. Study Design 3: collect all urine starting after the first dose and continuing through 16 hours post second dose administration. Record the volume of urine excreted. Collect a ~10 mL sample and store in 15 mL polypropylene falcon tubes for storage at -70°C until analysis.
- r. Collect ~ 2 mL of saliva. Instruct participant not to eat or drink for 30 minutes prior to beginning to spit.
- s. Remove sweat patches
  - i. For Study Design 1, remove one sweat patch 12 and 24 hours post drug administration. Place sweat patch in labeled ziplock bag for storage at -70°C until analysis.
  - ii. For Study Design 2, remove one sweat patch 8 and 12 hours post drug administration. Place sweat patch in labeled ziplock bag for storage at -70°C until analysis.

- iii.* For Study Design 3, remove one sweat patch 8 and 16 hours post second drug dose administration. Place sweat patch in labeled ziplock bag for storage at -70°C until analysis.
    - t.* Obtain end of study electrocardiogram reading. Send to cardiologist for interpretation.
    - u.* The research team will ask the participant to fast for 2 hours after drug administration. After this 2-hour mark, the participant is free to eat and drink as desired. Document all meal times and content. Collect food receipts when available. The following are scenarios where the research team may deviate from fasting for 2 hours post-administration:
      - i.* A participant may request to take atomoxetine with a small amount of soft food (e.g. pudding, applesauce, etc.) to aid with capsule swallowing. Document the food and approximate volume the participant used to aid with capsule swallowing (e.g. participant took capsule with ~1 teaspoon of chocolate pudding).
      - ii.* If participant reports GI upset, a small snack may be given to alleviate symptoms, even in the event that the fasting time has not been completed. Document GI upset as an adverse event in the adverse events log. If snack is given, document the snack time and content.
      - iii.* Fasting will not be required for participants taking medication in the evening who are participating in an overnight pharmacokinetic study. The research team does not believe it is feasible or expect a child to fast for 8-12 hours while awake.
      - iv.* If participant is assigned Study Design 3, fasting prior to and/or after the second dose of medication will not be required. The research team does not believe it is feasible to expect a child to fast prior to both the first dose and second dose.
    - v.* Perform assessment of attention tasks (Pupillometry during Posner's Cuing Task). Further details can be found in Appendix H.
    - w.* Perform Tanner Staging. The participant does not need to have Tanner Staging if this was performed previously within 4 weeks prior of Research Visit 3 or if the participant has already reached maximum stage in a prior Tanner staging exam.
    - x.* Administer end of study psychometric questionnaires:
      - i.* Screen for Child Anxiety Related Disorders (SCARED parent and participants  $\geq$  8 years old informant).

- ii.* Barkley's Sluggish Cognitive Tempo (SCT) (parent informant).
    - iii.* Behavior Rating Inventory of Executive Function (BRIEF) (parent informant. Teacher informant is optional).
  - y.* Administer Dietary Survey Questionnaire (participant informant).
- z.* Please note that the SCARED and the BRIEF are validated tools that are used to aid the Study Physician in determining treatment response. Use of different versions of these questionnaires are permissible to aid the Study Physician, in addition to clinical impression, with medication management and determination of response.
  - aa.* Assess for adverse events. Document in Adverse Events log.
  - bb.* Determine and document participant's adherence to ATX medication regimen.
    - i.* High adherence is defined as the participant taking  $\geq$  80% of their scheduled doses
    - ii.* Medium adherence is defined as the participant taking between 40 – 79% of their scheduled doses.
    - iii.* Low adherence is defined as a participant taking  $<$  40% of their scheduled doses.

11.1.1.1 Add compensation to participant's Greenphire account.

## **10. ADHD Care Following Conclusion of the Study**

Research personnel will call research participants and/or their parents two weeks ( $\pm$  1 week) following study conclusion or withdrawal from the study to check if any adverse events occurred in the interim. The research team will also take the opportunity to re-educate the family if a taper of medication was needed. This information will be documented on the 2-week Post-Study Completion Check CRF.

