## 5.2 Drug Handling

The study drug, ATX, will be stored, prepared, labeled, and dispensed by the CMH Investigational Drug Service (IDS) pharmacy. Study file documentation, accountability, and records for dispensing of atomoxetine will be maintained by IDS pharmacy personnel.

The study physician will submit a signed and dated prescription for ATX to IDS Pharmacy. Alternately, designated study personnel will deliver a prescription that has been signed and dated prescription by the study physician to IDS Pharmacy. A copy of all prescriptions will be retained in the participant's study binder. IDS Pharmacy will deliver the ATX prescription to the PCRU for Research Visit 2. Subsequent prescriptions for ATX will be filled as needed and will typically occur in conjunction with 6-week, 12-week, and 18-week visits. Medication refills may also occur outside of the 6-week, 12-week, and 18-week visits. Medication refills may be handed off or delivered to the participant to reduce foot traffic at Children's Mercy Hospital, as needed. Dose adjustments may also occur outside of the 6-week, 12-week, and 18-week visits.

All investigational drug will be returned to the study team at the end of the study for disposal by the IDS pharmacy, unless the child and their family would like to continue using ATX. In addition, if the participant would like to discontinue the study drug, but he or she will require an ATX wean to reduce risk of side effects from abrupt discontinuation as directed by his or her study physician, the participant may keep the remaining drug to complete this wean.

Refer to the Investigational Drug Service Policy and Procedure (Last Revision 04/2020) for the standard operating procedure (SOP) outlining details regarding the control of the study drug used in this protocol. Transportation of study drug will be handled by both IDS pharmacy and study personnel. Refer to the Investigational Drug Product Transport Policy (Last Revision 12/2019.) The locations of drug transportation and how this will be conducted are summarized below. Further details for drug handling may be found in Appendix J, "Study Drug Timeline."

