- k. If it is determined that the participant was previously taking and subsequently discontinued any of the following medications (see below) prior to notification of study opportunity, an appropriate time to administer baseline questionnaires and to begin ATX intervention must be determined.
  - i. ADHD medication other than a stimulant, e.g. ATX or  $\alpha_2$ -agonists
  - ii. Selective Serotonin Reuptake Transporter Inhibitor (SSRI)
  - iii. Selective Serotonin/Norepinephrine Reuptake Transporter Inhibitor (SNRI)
  - iv. Any medication that could reasonably be expected to affect neurotransmitter concentrations, such as anxiolytics, antiepileptics, antipsychotics.
  - v. A CYP2D6 inhibitor
  - vi. The following table will be used as guidance for when to administer baseline questionnaires (i.e. return to baseline neurotransmitter levels and/or behavior) and when to begin ATX therapy (i.e. drug and/or active metabolites excreted from participant). However, this only addresses the most common medications that children with ADHD or behavioral concerns are likely to be trialed on.
    - 1. The time indicated in “Medication Washout Interval,” is the minimum amount of time needed for medication to be removed and thus, the amount of time needed before beginning ATX intervention.
    - 2. Administering baseline questionnaires relates to estimating when the participant is likely to return to baseline behavior, which could be longer than the time needed for drug to be removed from systemic circulation. When it is noted that the, “length of pharmacodynamic effects can be variable,” the research team must rely on parent, teacher, and/or participant report of symptoms and function. Evaluation of the participant’s medication chart may be also assessed for this information.
  - vii. A detailed literature search must be conducted for medications not listed here. The process by which this occurs will be described in more detail in Appendix O.

Medication Class/Group	Examples *also CYP2D6 inhibitor (indication)	When to Administer Baseline Questionnaires	Medication Washout Interval (time expected for drug to be removed from systemic circulation)
ADHD Medications (non-stimulants)	atomoxetine	2-4 weeks	CYP2D6 genotype dependent (2- 4 weeks)
	clonidine (sleep)	1-2 weeks	CYP2D6 genotype dependent (1-2 weeks)
	clonidine (ADHD)	2-4 weeks	CYP2D6 genotype dependent (2-4 weeks)
	guanfacine (sleep)	1-2 weeks	May be CYP2D6 genotype dependent (1-2 weeks)

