**See the Schedule of Events (SOE) table below outlining all of the above procedures by visit.**

SHORT TITLE: ATX-PBPK-PD-Clinical Outcomes (U54)

Schedule of Events	Prescreen	Research Visit 1* θ	Intake with Study Physician ψ	Research Visit 2*	Research Visit 3*	6-Week Visit with Study Physician ψ	12-Week Visit with Study Physician ψ	18-Week Visit with Study Physician ψ	Research Visit 4*	2-week Post-Study Check
Time point	N/A	N/A	N/A	Start Med/Day 0	Day 0 + at least 2 weeks ε	Day 0 + 6 weeks and after RV3	6-Week Visit with Study Physician + 6 weeks	12-Week Visit with Study Physician + 6 weeks	After 18-Week Visit	After Research Visit 4
Visit Window	N/A	N/A	N/A	N/A	See note €	± 2 weeks	± 2 weeks	± 2 weeks	N/A	± 1 weeks
Type of Visit/Event	Phone	Phone/In Person	In person/telehealth	In Person	In Person	In person/telehealth	In person/telehealth	In person/telehealth	In Person	Phone
Potential Participant Identified	X									
Introduce the Study	X									
Schedule Research Visit 1	X									
Obtain Consent or Permission/Accent		X 								
Obtain participant continued assent (verbal)				X	X				X	
Document continued assent in research note				X	X				X	
Provide U54 Study Booklet		X								

SHORT TITLE: ATX-PBPK-PD-Clinical Outcomes (U54)

Schedule of Events	Prescreen	Research Visit 1* θ	Intake with Study Physician ψ	Research Visit 2*	Research Visit 3*	6-Week Visit with Study Physician ψ	12-Week Visit with Study Physician ψ	18-Week Visit with Study Physician ψ	Research Visit 4*	2-week Post-Study Check
Needlestick/Pill Swallowing Questions		X								
Explain and Begin Washout (if needed)		X								
Demographic Data		X								
Prior/Concomitant Meds		X		X	X	X	X	X	X	
Prior Medical History		X								
Vital Signs		X		X 	X 				X 	
Physical Exam		X	X	X	X	X	X	X	X	
Electrocardiogram		X							X	
Tanner Staging (optional)		X		X	X				X	
Pregnancy Test		X		X	X				X	
Safety Laboratory Tests (CBC w/diff; Base Met; LFTs; UA w/micro)		X		X	X				X	
Confirm ADHD Diagnosis			X							
Assess for Comorbidities			X			X	X	X		

SHORT TITLE: ATX-PBPK-PD-Clinical Outcomes (U54)

Confirm ATX appropriateness for participant			X							

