## SHORT TITLE: ATX-PBPK-PD-Clinical Outcomes (U54)

Screen for Child Anxiety and Related Disorders (SCARED) – child ( $\geq 8$ )		X							X	
Schedule of Events	Prescreen	Research Visit 1* θ	Intake with Study Physician ψ	Research Visit 2*	Research Visit 3*	6-Week Visit with Study Physician ψ	12-Week Visit with Study Physician ψ	18-Week Visit with Study Physician ψ	Research Visit 4*	2-week Post-Study Check
NICHQ Vanderbilt Assessment Scales – parent			X 			X	X	X		
NICHQ Vanderbilt Assessment Scales – teacher			X 			X	X	X		
Child Behavior Checklist – parent			X 						X	
Child Behavior Checklist – teacher			X 						X	
Strengths and Difficulties Questionnaire – parent			X 						X	
Strengths and Difficulties Questionnaire – teacher			X 						X	
Medication Side Effects – parent			X 			X	X	X		
Medication Side Effects – teacher			X 			X	X	X		

SHORT TITLE: ATX-PBPK-PD-Clinical Outcomes (U54)

School Intervention Questionnaire			X 					X		
Child Medical History Questionnaire			X 							
Schedule of Events	Prescreen	Research Visit 1 *	Intake with Study Physician ψ	Research Visit 2 *	Research Visit 3 *	6-Week Visit with Study Physician ψ	12-Week Visit with Study Physician ψ	18-Week Visit with Study Physician ψ	Research Visit 4 *	2-week Post-Study Check
Clinical Global Impression			X			X	X	X		
Adherence Check					X	X	X	X	X	X 
Adverse Events		X	X	X	X	X	X	X	X	X
Take Back U54 Study Booklet/Survey									X	

 Execution of permission/assent may occur via phone to allow participants to fill out psychometric questionnaires.

 Heart and blood pressure to take with each blood draw.

 These events occur prior to the visit for preparation.

 These phone calls occur in 2 parts.

 These questionnaires must be completed by the Intake Visit; however, they may be assigned at Research Visit 1 to allow participants ample time to complete.

 For participants recruited from Track 4, these questionnaires are assigned immediately after consent has been obtained.

 For participants who require a taper off medication.

\*These visits will occur in the Pediatric Clinical Research Unit (PCRU).

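### The last scheduled adverse-event contact is timed from study end, not from the last atomoxetine dose, so for children who taper it can fall before or soon after the drug is stopped

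*Combined protocol and SAP*

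**What the plan says.** **The call.** Section 11.2, item 10 (ADHD Care Following Conclusion of the Study) has research staff telephone the family two weeks (± 1 week) "following study conclusion or withdrawal from the study to check if any adverse events occurred in the interim", and record the answers on the "2-week Post-Study Completion Check CRF". Staff also use the call to go over taper instructions again where a taper was needed. The Schedule of Events places it "After Research Visit 4". It is the last column with an adverse-event mark.

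**The last dose.** The Research Visit 4 procedures include the step "Administer dose of atomoxetine according to prescription", so a completer's last dose is no earlier than that visit. Section 5.2 provides for the child who wants to stop but for whom "he or she will require an ATX wean to reduce risk of side effects from abrupt discontinuation", and lets that child keep the remaining capsules. Section 11.5 lists stopping or weaning among the end-of-study options. Footnote 7 of the Schedule of Events adds an adherence check to the post-study call: "For participants who require a taper off medication". No taper length is given.

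**The washout interval.** The prior-medication table in section 11.2 (Research Visit 1 – Part 1) says its interval "is the minimum amount of time needed for medication to be removed". The atomoxetine entry is "CYP2D6 genotype dependent (2- 4 weeks"), and the same row gives 2-4 weeks before baseline questionnaires.

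**The steady-state assumption.** Section 11.1 (Research Visit 3) takes steady state as reached after two weeks of routine dosing, with no exception by genotype.

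**The concern.** A closing safety contact should come late enough to ask about what happens when the drug is stopped. The protocol recognises discontinuation effects as the reason for a wean, yet it times its last scheduled question from the end of the study. For a child still weaning, study end and drug end are different dates, and the call follows the wrong one.

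What is at stake is completeness of safety data. Section 20.1 lists adverse-event reporting as one of four ways clinical outcomes will be analysed, and section 17.0 names emotional lability and reports of suicidal ideation among the risks. Section 11.1 notes slower clearance in poor metabolisers, so cover relative to clearance is thinnest in a genotype group that the trial sets out to study. No power figure or efficacy analysis is affected.

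**Working it through.** The plan states no figure for this coverage, so there is none to reproduce. The check is interval arithmetic.

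**Inputs**
- Call time after study end, C: 2 ± 1 weeks, so 14 − 7 = day 7 to 14 + 7 = day 21 (section 11.2, item 10; Schedule of Events).
- Atomoxetine interval after the last dose, W: 2-4 weeks, so 14 to 28 days (washout table).
- Taper after study end, T: not in the documents. I use T = 0, and an assumed range of 1-4 weeks (7 to 28 days) for illustration.
- Last dose of a completer who does not taper: taken as study end, because a dose is given at Research Visit 4.

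**Formula.** Days between the call and the end of the interval: G = T + W − C. A positive G is time with no scheduled question.

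**No taper (T = 0)**

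| Call | W = 14 | W = 28 |
|---|---|---|
| Day 7 | 14 − 7 = 7 | 28 − 7 = 21 |
| Day 14 | 14 − 14 = 0 | 28 − 14 = 14 |
| Day 21 | 14 − 21 = −7 (covered) | 28 − 21 = 7 |

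At the short end of the table, only calls on days 7-13 fall inside the interval. At the long end, no permitted call reaches day 28.

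**With a taper.** T adds to every cell.
- Smallest gap in the assumed range: 7 + 14 − 21 = 0 days.
- Largest gap: 28 + 28 − 7 = 49 days (7 weeks).
- The call precedes the last dose whenever T exceeds C. That needs a taper longer than 7 days for the earliest permitted call and longer than 21 days for the latest.
- Supply does not rule this out. Appendix J prepares a 6-8 week prescription before the 18-week visit, and the child may keep what remains.

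**Cross-check against the steady-state assumption.** Section 5.1 models clearance as first order. Under such kinetics, the shortfall from steady state after two weeks of dosing equals the fraction remaining two weeks after stopping. If two weeks is enough to reach steady state, it is also enough for near-complete removal. The nominal day-14 call then covers a child who stops without a taper. This argument does not reach calls on days 7-13. It does not address the separate 2-4 weeks for return to baseline, and it does nothing for a child whose last dose comes weeks after study end.

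**The case against.** **The 2-4 weeks is borrowed.** It comes from guidance on medication stopped before baseline and was not written as a standard for adverse-event follow-up. With the two-week steady-state assumption, it makes the nominal call look adequate when there is no taper. This largely stands, and it is why the no-taper gap is small. The table is nevertheless the only atomoxetine washout interval in the protocol, and nothing says why it would not apply at study end.

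**A call need not follow full washout to be useful.** Effects that begin as concentrations fall may already be present. This stands for early effects after an abrupt stop.

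**Other routes exist.** A reader might infer that later events would be recorded only if a family volunteers them. Section 4.2 does not support that: it also lists hospital-admission notifications to the study physician and reports at clinic visits, and section 11.5 allows the study physician to continue care. These routes are passive, however, and none schedules a question after the call. Section 16.2 follows adverse events to resolution, which helps with known events but does not look for new ones.

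**Timing of the taper.** A reader might also infer that for tapering children the call always precedes the last dose. The documents give no taper length, item 10 refers to the taper in the past tense, and footnote 7 does not say that it is still running. The supported statement is that it can.

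**The call has a second job.** Simply moving it later would take away the scheduled taper re-education and adherence check. This stands and shapes the remedy.

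**Unseen documents.** The DSMB Charter, DSMB Protocol and institutional reporting policy are cited but not included, so a longer reporting period there cannot be excluded.

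**Conclusion.** The point holds, chiefly for children who taper. Scheduled adverse-event questioning is tied to study end, and for these children it can finish before or soon after the last dose. By how much depends on a taper length that the protocol does not state; on the assumed 1-4 weeks, the shortfall against the plan's own interval runs from 0 to 7 weeks.

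For children who stop without a taper, the shortfall is at most 21 days and often nil. It concerns mainly calls on days 7-13, or slow metabolisers at the upper end of the table. The claim that every stopping child is left uncovered would go too far: an abrupt stop with two-week clearance and a call at week 2 or 3 is covered. A child who stopped well before formal withdrawal may also have longer cover than the arithmetic shows. Children who stay on atomoxetine are not affected.

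This rests on the washout table being relevant at study end and on no longer reporting period existing in the documents not supplied. It is a cheap improvement, minor to moderate in severity.

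**What to change.** Reconcile section 11.2 item 10, the Schedule of Events with its footnote 7, the atomoxetine row of the washout table, and section 5.2:
- For children who stop atomoxetine, anchor the final adverse-event question to the last dose, including the end of any taper. Make its timing consistent with the plan's own washout interval, or state why a shorter period suffices, for example by reference to the two-week steady-state assumption.
- Keep the present two-week call for everyone, with its taper re-education and adherence check.
- Children still tapering at that call get one brief repeat call from the same staff. Record the date of the last dose so that the call can be timed.

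Whether and how a child tapers, and every other clinical rule, stays with the study physicians.

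The cost is a sentence in item 10, a change to the Schedule of Events, one extra short call for tapering children, slightly later close-out and a few more families not reached.
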